3.3 Other Outcomes of Interest

n.a.

3.4 Safety Outcomes

No other specific safety outcomes than the previous described (postoperative hypersensitivity, loss of vitality, loss of restoration, tooth fracture, tooth loss) will be evaluated.

4. CLINICAL INVESTIGATION DESIGN

4.1 General clinical investigation design and justification of design

A double blind (patient and evaluator), randomized, controlled, split mouth clinical trial is planned for TM Flow used to restore NCCL. The split mouth design allows the comparison of the two restorative materials under the same clinical circumstances. The materials are being exposed to the same oral conditions (microbiota, oral hygiene, nutrition, saliva, chewing forces and if given parafunctions). The evaluation of postoperative hypersensitivity benefits from the study design, since this parameter is influenced by the individual perception on pain which vary widely among individuals. The risk for these interindividual variations is minimized by the use of the split mouth study design.

66 patients will be included in this clinical investigation. Each patient will receive 2 restorations. The restoration belonging to the test group will be restored with TM Flow. The second restoration belonging to the control group will be restored with Tetric EvoFlow. The clinical procedure for both flowable composites is very similar, only the material differs. The randomization process will be performed electronically by the EDC platform Castor, which will also be used for the collection of data. The restorations will be placed by 6 trained operators. Each operator will place at least 10 fillings. The evaluation of the restorations will be performed by an evaluator, that will be blinded and that has no information about the assignments of the restorations to each group.

The duration of the clinical trial is 60 months. After the placement of the restorations, they will be evaluated at a baseline recall after 7-10 days and then after 1, 6, 12, 24, 36 and 60 months. At every recall postoperative sensitivity, teeth vitality, retention rate of restorations, color match, surface luster and texture, marginal integrity, form and contour, and contact points will be assessed according to FDI criteria (Hickel et al., 2022). Additionally, the margins of the restorations will be assessed by SQUACE (SemiQUAntitative Clinical Evaluation) according to the FDI criteria.

The participants are recruited from the existing patient pool of the internal practice of Ivoclar Vivadent AG and are thus employees of the company. No active recruiting measures are taken. Each participant has the right to refuse participation in the clinical trial at any time.

4.2 Methods for minimising bias

4.2.1 Randomisation

Randomisation is performed electronically by Castor. Castor uses a validated variable block randomization model with optional stratification.

4.2.2 Blinding procedures

The evaluator will be blinded. The evaluator has only access to the recall eCRFs which contain no information regarding assignment of the restorations to the study groups. The patient is also blinded. The operator will not communicate the material which is used to treat the lesion. As long as the patient is lying on the dental chair it does not see the material, which is applied, therefore the patient does not know which tooth has received which material.

4.2.3 Other methods for minimising bias

n.a.

4.3 Unblinding Procedures (Code break)

The operators and the PI are not blinded. Only the evaluator and the patients are blinded. If necessary, the evaluator gets information about the group allocation from the PI (for instance premature termination of the study).

5. CLINICAL INVESTIGATION INTERVENTION

5.1 Identity of the medical device under investigation

TM Flow is a flowable, light-curing, radiopaque composite (200% AI) for the direct restorative treatment of anterior and posterior teeth. TM Flow cures with light in the wavelength range of 400–500 nm and can be applied in layers of up to 4 mm.

5.1.1 Experimental Intervention (medical device)

The direct filling therapy of an NCCL with a composite often in flowable consistency is an every day procedure for most dentists. The placement of this kind of filling is part of the basic training during dental medicine study. It is also described in many videos which are freely available. In the properties relevant to the application, test and control material differ only in the fact that TM Flow can be applied in thicker increments up to 4 mm compared with Tetric EvoFlow with 2 mm increment size and in slight difference in the consistency.

For a patient it is often difficult to differentiate the exact tooth, which is responsible for a tooth ache. Therefore, experimental and control intervention can only be done at the same treatment session if the two teeth are located in different quadrants. Otherwise only one tooth can be treated in one visit. The second tooth can only be treated if the first tooth did not show any sign of postoperative sensibility or after the symptoms of postoperative sensibility have disappeared. After the first intervention at least the baseline visit needs to be waited for.

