Inclusion / exclusion criteria:	
Inclusion criteria:
 
 • Informed Consent signed by the subject • Age: 18-65 years • 2 NCCL needing treatment, comparable in extend and size, preferably located in different quadrants • Vital teeth, regular sensitivity • Sufficient language skills • No active periodontitis • Preoperative VAS values < 3 regarding tooth sensitivity on biting. Tooth sensitivity on temperature or touching (tooth brushing, probing) originating in the area of the NCCL is accepted. • Subject wishes to have a restoration as part of the study (written declaration of consent after detailed explanation) 
Exclusion criteria:
 
 • Not completed hygiene phase or poor oral hygiene • Sufficient isolation of the cavity not possible • Patients with a proven allergy to one of the ingredients (methacrylates) • Patients with severe systemic diseases • Periodontally insufficient dentition • Pregnancy • Part of the development project team of TM Flow • Staff of the study management team • Staff of the internal clinic
Measurements and procedures:	
Each participant receives two different fillings (test- and control material) in two different teeth. The fillings are assessed according to selected FDI criteria at baseline (7-10 days after filling placement) and after 1, 6, 12, 24, 36 and 60 months. At each of these times points, the sensitivity is recorded using a visual analogue scale. The results are documented by intraoral images.

Intervention:	
The newly developed flowable composite TM Flow will be used for the restoration of NCCLs in the test group. The treatment workflow is very similar to other flowable composites.

Control intervention (if applicable):	The well-established Tetric EvoFlow will be used for the restorations of NCCLs in the control group. This material has been routinely used for such treatments in the internal clinic of Ivoclar Vivadent AG for many years.
Number of subjects with rationale:	66 patients are receiving 2 restorations because of the split-mouth study design.
Duration of the investigation:	60 months for each patient (recruiting phase 4 months)
Investigation schedule:	January 2024 First-subject-In December 2029 Last-subject-Out

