USADE	Unanticipated Serious Adverse Device Effect

INVESTIGATION SCHEDULE

Study Periods	Screening	Treatment, Intervention Period	Follow-up							
Visit	0	1	2	3	4	5	6	7	8	
Time (hour, day, week)	-3- (-30) d	0 d	7-10 d	1 m	6 m	12 m	24 m	36 m	60 m	
Patient Information and Informed Consent	x									
Medical History	x									
In- /Exclusion Criteria	x									
Tooth Examination	x									
Pregnancy Test (only in case of uncertainty)	x									
Vitality test	x	x	x	x	x	x	x	x	x	
VAS for tooth sensitivity		x	x	x	x*	x*	x*	x*	x*	
Preparation of tooth,		x								
Randomization		x								
Placement of restoration (test or control)		x								
Primary Variables			x	x	x	x	x	x	x	
Secondary Variables			x	x**	x	x	x	x	x	
Photographs	x	x	x	x	x	x	x	x	x	
Adverse events and device deficiencies		x	x	x	x	x	x	x	x	

* Assessment will only be done if there is a patient complaint for paraesthesia or pain

** Not all variables will be assessed (only fracture of material, surface luster, color match)

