3. CLINICAL INVESTIGATION OUTCOMES

3.1 Primary Outcome

The primary outcome in this clinical trial is the FDI criteria - B3 pulpal hypersensitivity and pulpal status (Hickel et al. 2022) 1 month after placing of the fillings. Postoperative hypersensitivity is considered an indicator of the response of a tooth (pulp) to the therapeutic procedure applied. Postoperative hypersensitivity can be observed within a short time after the treatment. Therefore, it is assessed for the first time at the baseline recall (after 7-10 days). The assessment of postoperative hypersensitivity includes questions about type and duration of pain, intensity of pain and on the stimulus inducing the pain. The subjective perception of the intensity of postoperative hypersensitivity caused by thermal stimuli and caused by occlusal forces (during biting) will be determined by the aid of a Visual Analog Scale (VAS). The VAS values are brought into relationship to the preoperative values. In the table below a description of the correlation between FDI grade and VAS values and clinical signs and symptoms is shown. Not all signs need to be present at one stage. The exact VAS values vary widely from patient to patient, depending on each individual's pain tolerance. Therefore, it is one of the factors influencing the FDI grade, but it is not directly correlated. Not all the described conditions have to be fulfilled to attribute an FDI score. Depending on the intensity and character of the pain, further therapy will be determined. Usually, postoperative hypersensitivity subsides spontaneously and no treatment is necessary. In case of very intense pain an immediate treatment is required. The application of a fluoride varnish is the first procedure of choice. If no improvement is achieved by this method, then the replacement of the restoration would be the next step. In the worst case, the pulp is severely inflamed, requiring endodontic treatment. If the postoperative hypersensitivity does not subside spontaneously or worsens after the applied treatment, the highest assessed FDI value is used for the statistical analysis.

For all participants a 1-month recall is planned to finally assess the postoperative hypersensitivity. The clinical experience of the evaluator is of major importance in the correct assessment of the FDI grade. In general, the rule applies, that in case of uncertainties the higher score is attributed.

FDI grade	1	2	3	4	5

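### In same-quadrant pairs, the first tooth's 1-month primary assessment can fall within the second tooth's own postoperative period, and neither treatment order nor the second tooth's visit clock is specified

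*Combined protocol and SAP*

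**What the plan says.** The inclusion criteria in the synopsis ask for "2 NCCL needing treatment, comparable in extend and size, preferably located in different quadrants". Different quadrants are a preference, so same-quadrant pairs can be enrolled.

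Section 5.1.1 gives the reason for separating such teeth: "For a patient it is often difficult to differentiate the exact tooth, which is responsible for a tooth ache". It follows that "experimental and control intervention can only be done at the same treatment session if the two teeth are located in different quadrants". Two conditions govern the second tooth. The first concerns symptoms: "The second tooth can only be treated if the first tooth did not show any sign of postoperative sensibility", or once such symptoms have gone. The second is a minimum wait: "After the first intervention at least the baseline visit needs to be waited for".

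Section 4.1 gives the timing of visits after placement: "they will be evaluated at a baseline recall after 7-10 days and then after 1, 6, 12, 24, 36 and 60 months". Section 3.1 sets the primary outcome as FDI criterion B3 one month after placement and says: "For all participants a 1-month recall is planned to finally assess the postoperative hypersensitivity".

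The Investigation Schedule has one treatment visit at day 0, where randomisation and placement both appear, and one series of recalls. It has no entry for a second placement visit. Section 4.2.1 describes variable block randomisation in Castor and does not mention the order in which the teeth are treated. Section 4.3 states that operators are not blinded.

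**The concern.** The reason given for the stagger, that pain is hard to localise, applies for as long as either tooth may hurt from its restoration. The mandatory wait protects only the first tooth's 7-10 day visit. The primary comparison is made at 1 month, and nothing requires the first tooth's 1-month assessment to be finished before the second tooth is filled. Pain from the second tooth could then be scored on the first tooth at the visit that decides the trial.

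Two features make this more than a matter of wording. The schedule does not show how a staggered second tooth reaches an assessment one month after its own placement. Order is also left open while operators know the materials, so nothing prevents order from being associated with material. If TM Flow were placed second more often, its pain could be credited to the control tooth, which would favour non-inferiority. The reverse order would work against it.

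**Working it through.** **1. The plan's own figure.** Inputs from 6.1 and 6.2: both proportions 0.024, margin 0.076, nuisance parameter 0.012, one-sided alpha 0.05, power 80%. Reading the nuisance parameter as the probability that both teeth are affected, each discordant cell is 0.024 − 0.012 = 0.012. For the paired score test (Nam):

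- Variance under the alternative: V1 = 0.012 + 0.012 = 0.024.
- Variance under the null: V0 = 2(0.00602) + 0.076 × 0.924 = 0.0823, where 0.00602 is the constrained estimate of the control-only cell.
- n = (1.645√0.0823 + 0.842√0.024)² / 0.076² = 62.8, rounded up to 63. Adding 3 drop-outs gives 66.

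The plan's 63 is reproduced, and this point does not change it.

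**2. The overlap.** Let g be the gap between placements and M the day of the 1-month visit. The minimum g is 7-10 days (5.1.1 with 4.1). M is taken as 28-31 days, which is an assumption.

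- Age of the second tooth at the first tooth's primary assessment: M − g, from 28 − 10 = 18 to 31 − 7 = 24 days.
- The second tooth's own 1-month point on the first tooth's clock: M + g, from 28 + 7 = 35 to 31 + 10 = 41 days, when the first tooth is already past 1 month.

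Any second placement before about day 28-31 overlaps; a later one does not. The grading table under 3.1 has categories for symptoms lasting more than a week and more than a month, so the plan itself allows for pain at 18-24 days. Section 3.1 also assigns the higher grade when the evaluator is unsure.

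**3. How often the symptom condition lengthens the wait.** At the planned rate, 1 − 0.024 = 97.6% of first teeth would have no hypersensitivity, so the condition would rarely delay the second placement.

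**4. The visit clock.** If all recalls ran from a single day 0, the 7-10 day recall would come no later than the second placement, and the 1-month recall would see the second tooth at 18-24 days or younger. Neither fits 3.1, which times the outcome from placement. Per-tooth timing fits 3.1, but the schedule does not show it.

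**5. What one event is worth.** Expected events per material: 0.024 × 63 = 1.5. One event wrongly added to or removed from one tooth moves the difference by 1/63 = 1.6 points. One event moved from one tooth to the other moves it by 2/63 = 3.2 points, or 3.2/7.6 = 42% of the margin.

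**6. How many pairs.** The documents give no share of same-quadrant pairs. Assuming 10-30% of 66, there are 6.6-19.8 such pairs, and at 2.4% they contribute 0.16-0.48 expected second-tooth events in the whole trial.

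**The case against.** The case on the other side has several good points.

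- **The wait is a floor.** A reader might infer that the first tooth's assessment always falls in the second tooth's postoperative period. The text says at least the baseline visit, and the second placement may come later. The overlap is permitted, and it occurs if the minimum gap is used, but it is not certain.
- **The symptom condition helps.** A reader might infer that misattribution returns in full. The first tooth has been found free of symptoms before the second is touched, so new pain has an obvious candidate source. B3 also draws on type and duration of pain, stimulus, pulp status and the vitality test. This reduces the risk but does not remove it, because the condition says nothing about pain that the second tooth causes later.
- **The endpoint is timed from placement.** A reader might infer that the plan directs an assessment of the second tooth at about three weeks. Sections 3.1 and 4.1 point to per-tooth timing. The schedule leaves a gap; it does not give that instruction.
- **No association of order with material is shown.** A reader might infer a bias in favour of TM Flow. The documents do not say that one material goes second more often. They only fail to prevent it.
- **The reversal example is a worst case.** With 63 pairs, a TM Flow-only/control-only split of 2/0 gives a one-sided 95% paired score (Tango) upper limit of 9.15%, which fails the margin. Crediting one of those events to the control tooth gives 1/1 and a limit of 5.43%, which passes. Under the planned cells a true 2/0 split has probability 1953 × 0.012² × 0.976⁶¹ ≈ 6%, before the chance that an affected pair is in the same quadrant and is misattributed.

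All five points limit the size and certainty of the effect. None closes the gap between the reason given for the stagger and the time it covers.

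**Conclusion.** The concern holds as a possibility that the written rules leave open. In same-quadrant pairs treated at the minimum gap, the first tooth's primary assessment falls on about day 18-24 of the second tooth, and the difficulty of localising pain is then present at the primary time point. The schedule does not show how the second tooth's 1-month assessment is reached, and order is not protected from association with material.

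The size of the effect is unknown, because it depends on the share of same-quadrant pairs, the actual gaps and the chance of misattribution, none of which the documents give. On the assumed 10-30% share, few events are exposed. The point still merits correction before such pairs are enrolled: the trial expects about 1.5 events per material, and one event credited to the wrong tooth is worth 3.2 of the 7.6 points in the margin. This rests on the planned rate of 2.4%, on 63 pairs and on a month of 28-31 days.

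**What to change.** 1. For same-quadrant pairs, have Castor allocate which tooth is treated first together with its material.
2. Record placement date and order for each tooth, and analyse the primary outcome at 1 month from each tooth's own placement.
3. Repeat the primary comparison in different-quadrant pairs only, as a prespecified sensitivity analysis. Allocating order keeps it from following material but does not stop pain being credited to the wrong tooth, so this analysis is still needed.
4. Reconcile the inclusion criterion, the Investigation Schedule, 3.1 and 5.1.1 on the stagger and on the visit clock for a staggered second tooth. The interval, the visits and the quadrant rule are for the sponsor and investigator to decide; none is proposed here.

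The cost is one Castor setting, two recorded fields per tooth, one extra table and the amended text. The sensitivity analysis will have fewer pairs and wider limits, so it should be read as a check on the primary result and not as a second test.

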5.1.2 Control Intervention (standard/routine/comparator)

See 8.1.1

6. STATISTICAL METHODS

6.1 Hypothesis

The Null Hypothesis (H_0) is that the proportion of postoperative hypersensitivity occurrence after the treatment with the new composite (P_{treat}) will be inferior to the treatment with an already established composite (P_{control}). The alternative hypothesis (H_1) is that the treatment with the new composite will be non-inferior to the standard treatment.

The non-inferiority difference is a predefined margin of difference between the new treatment and the control treatment. The upper limit of the clinically acceptable proportion of postoperative hypersensitivity is 10% (proportion determined by experience). The actual proportion of patients experiencing postoperative hypersensitivity after a direct restorative treatment at the study site (internal clinic of Ivoclar Vivadent AG) is 2.4%. Therefore, the calculated non-inferiority difference is 7.6%.

Split-mouth design with a one-sided non-inferiority hypothesis:

$$H_1: P_{\text{treat}} - P_{\text{control}} < 7.6\%$$

$$H_0: P_{\text{treat}} - P_{\text{control}} \geq 7.6\%$$

6.2 Determination of Sample Size

The sample size calculation was performed by [name] (biostatistician) from the Clinical Trials Unit of the Kantonsspital St. Gallen. Her CV and calculations can be provided upon request.

The power was calculated using PASS Version 21.0.5 (PASS 2021 Power Analysis and Sample Size Software (2021). NCSS, LLC. Kaysville, Utah, USA, [ncss.com/software/pass.](http://ncss.com/software/pass/)).

Using the parameters listed in Table below, a sample size of 63 subjects achieves 80% power at a significance level of 0.05.

Considering a drop-out of 3 patients, it is planned to include 66 patients in this study.

Parameters used for the sample size calculation.

P_{treat}	P_{control}	Actual difference	Non-inferiority difference	Nuisance parameter	Target alpha	Power	Sample size
0.024	0.024	0*	0.076	0.012	0.05	0.80	63

*It is expected that the treatment with the novel composite leads to a comparable proportion of patients with postoperative hypersensitivity in comparison to the control treatment.

6.3 Statistical criteria of termination of the investigation

If 6 or more patients show a postoperative hypersensitivity of FDI grade 4 or 5 in test or control group the study will be terminated.

6.4 Planned Analyses

The IBM SPSS Version 25 software package will be used for data analysis.

The level of postoperative hypersensitivity between the control and the test group will be analysed.

6.4.1 Datasets to be analysed, analysis populations

The data collected of all eligible participants that received two final fillings will be used for the statistical data analysis.

6.4.2 Primary Analysis

Regarding the primary outcome, the interim analysis will be done at baseline. The final analysis of the primary outcome will be done after 1 month. It will be evaluated if the difference between postoperative hypersensitivity rate (FDI criterium B3) in test and control group is lower than the predefined non-inferiority margin (7.6%). The analysis will be done by the principal investigator within 3 months after OTCS 36419419, Version 3.0 of 17.01.2024

the collection of the data.

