Investigator(s):	
 - [name], [name] - [name], [name] - [name], [name] - [name], [name] - [name], [name] - [name], [name] - [name], [name]
Investigational Site(s):	
This is a single center study.
 
R&D Clinic Ivoclar Vivadent AG [name] Liechtenstein

Statistical considerations:	
The sample size was calculated for a split-mouth design with a one-sided non-inferiority hypothesis (target alpha 5%; power 80%).
 
The obtained data of the test group will be compared with the data from the control group.

Compliance statement:	This investigation will be conducted in compliance with the CIP, the current version of the Declaration of Helsinki, ISO14155, ICH-GCP (as far as applicable) as well as all national legal and regulatory requirements.

ABBREVIATIONS

AE	Adverse Event
ADE	Adverse Device Effect
ASADE	Anticipated Serious Adverse Device Effect
ASR	Annual Safety Report
CA	Competent Authority (e.g. Amt für Gesundheit, Liechtenstein)
CEC	Competent Ethics Committee
CIP	Clinical investigation plan
ClinO	Ordinance on Clinical Trials in Human Research (in German KlinV, in French Oclin, in Italian OSRUM)
ClinO-MD	Ordinance on Clinical Trials with Medical Devices (in German: KlinV-Mep, in French: Oclin-Dim, in Italian: OSRUM-Dmed)
CRF	Case Report Form (pCRF paper CRF; eCRF electronic CRF)
DD	Device Deficiency
DMC / DSMC	Data Monitoring Committee, Data Safety Monitoring Committee
FDI	Fédération Dentaire Internationale
Ho	Null hypothesis
H1	Alternative hypothesis
HRA	Federal Act on Research involving Human Beings (in German: HFG, in French: LRH, in Italian: LRUM)
IB	Investigator's Brochure
ICF	Informed Consent Form
ICH-GCP	International Council for Harmonisation – guidelines of Good Clinical Practice
IFU	Instruction For Use
ISF	Investigator Site File
ISO	International Organisation for Standardisation
ITT	Intention to treat
MedDO	Medical Devices Ordinance (in German: MepV, in French: Odim, in Italian: Odmed)
MD	Medical Device
MDR	Medical Device Regulation (EU) 2017/745 of 5 April 2017
NCCL	Non-carious cervical lesions
PI	Principal Investigator
SADE	Serious Adverse Device Effect
SAE	Serious Adverse Event
SDV	Source Data Verification
SNCTP	Swiss National Clinical Trials Portal
SOP	Standard Operating Procedure

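### Section 6.4.2 names no test, confidence limit or paired method for the non-inferiority decision, and at the expected event counts the choice of method can reverse the result

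*Combined protocol and SAP*

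**What the plan says.** - **Decision rule (6.4.2).** The analysis evaluates whether "the difference between postoperative hypersensitivity rate (FDI criterium B3) in test and control group is lower than the predefined non-inferiority margin (7.6"%). The principal investigator carries it out within three months of data collection.
- **Hypotheses (6.1).** H0 is a difference of 7.6 points or more. "The alternative hypothesis (H_1) is that the treatment with the new composite will be non-inferior to the standard treatment". The design is split-mouth and one-sided.
- **Error level (Synopsis, Statistical considerations).** "The sample size was calculated for a split-mouth design with a one-sided non-inferiority hypothesis (target alpha 5%; power 80"%).
- **Sample size (6.2).** With 2.4% in both groups and a nuisance parameter of 0.012, "a sample size of 63 subjects achieves 80% power at a significance level of 0.05". Enrolment is set at 66 to allow for three drop-outs.
- **Analysis (6.4 and 6.4.1).** The software is SPSS 25 and "The level of postoperative hypersensitivity between the control and the test group will be analysed". The analysis set is eligible participants with two final fillings. Sections 6.4.3 to 6.4.5 add nothing on method.
- **Endpoint (3.1).** "The primary outcome in this clinical trial is the FDI criteria - B3 pulpal hypersensitivity and pulpal status", graded 1 to 5 and taken at 1 month. No section says which grades make up the rate. Section 6.3 singles out grades 4 and 5, but only for stopping: "6 or more patients show a postoperative hypersensitivity of FDI grade 4 or 5 in test or control group".

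**The concern.** A non-inferiority claim needs a rule that bounds the chance of accepting a material that is worse by the margin. The plan sets that bound at 5% when it sizes the trial, but the decision sentence compares the rate difference itself with 7.6% and gives no allowance for sampling error. The hypotheses, the alpha and the nuisance parameter suggest that a formal paired test was intended. The reader still cannot tell which one, and paired methods differ widely when events are this rare.

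This is the primary claim of a pivotal study run for conformity assessment. At 2.4%, about 63 × 0.024 = 1.5 control events are expected, so one or two teeth decide the outcome. The plan does not say who fixes the method or when. It says only that the analysis is done by the principal investigator, who is not blinded (4.3), and that data are compared after every recall (6.4.4), with a look at the primary outcome at baseline (6.4.2).

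**Working it through.** **Inputs.** Margin D = 0.076 (6.1). One-sided alpha 0.05 and power 0.80 (Synopsis, 6.2). Rates 0.024 and 0.024, nuisance parameter 0.012, n = 63, 66 enrolled (6.2). Write b for TM Flow-only pairs and c for control-only pairs. All rates assume a yes/no event, which the plan does not define.

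**1. The plan's own 63.** Asymptotic sample size for the paired score test (Tango/Nam), taking 0.012 as each discordant cell and a true difference of 0:

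n = [(1.645·√v0 + 0.842·√v1) / D]²

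- Restricted estimate of the control-only cell under H0: q = 0.00602.
- v0 = 2q + D(1 − D) = 0.01204 + 0.07022 = 0.08226.
- v1 = 0.012 + 0.012 = 0.024.
- n = [(0.4718 + 0.1304) / 0.076]² = 62.8, hence 63.

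Other readings do not return 63:

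| Reading of discordance | Score | Wald |
|---|---|---|
| Each cell 0.012 | **63** | 26 |
| Total 0.012 (each cell 0.006) | 52 | 13 |
| Independent teeth (each cell 0.024 × 0.976 = 0.0234) | 83 | 51 |

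Reading 0.012 as the probability that both teeth have an event gives the same cells as the first row (0.024 − 0.012 = 0.012). Methods other than score and Wald were not tried.

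**2. One table, two answers.** Take b = 2, c = 0, n = 63 (hypothetical), so d = 2/63 = 0.0317.

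- Wald upper limit: d + 1.645·√{[(b + c)/n − d²]/n} = 0.0317 + 1.645·√(0.03074/63) = 0.0317 + 0.0363 = 0.0681. This passes.
- Score statistic at the margin: with c = 0 the restricted estimate is 0, so z = (2 − 63 × 0.076)/√(63 × 0.076 × 0.924) = −2.788/2.103 = −1.325. It does not reach −1.645. The inverted upper limit is 0.0915 (0.09149). This fails.
- Exact unconditional paired test: p = 0.13. This fails.
- With 66 pairs the limits are 6.50% (Wald) and 8.75% (score), so the split remains.

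With no control-only events, the most TM Flow-only events that still pass are 2 under Wald and 1 under score.

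**3. False non-inferiority at a true difference of 7.6 points.** Exact trinomial enumeration, control-only cell 0.012:

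| Rule | n = 63 | 64 | 65 | 66 |
|---|---|---|---|---|
| Wald limit < 7.6% | 9.8% | 9.2% | 8.7% | 8.3% |
| Paired score limit < 7.6% | 3.7% | 3.5% | 5.1% | 4.8% |
| Exact unconditional test | 3.3% | 3.5% | 2.9% | 4.8% |
| Point estimate < 7.6% | 46.9% | 45.7% | 44.5% | 59.3% |

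With the control-only cell varied from 0 to 0.0234, the ranges are 7.4–13.3% (Wald), 3.3–5.1% (score) and 2.9–4.8% (exact). For the point rule they are 44–47% at 63 to 65 pairs and 58–61% at 66. The jump arises because 5/66 = 7.58% falls just under the margin.

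**4. How often the choice matters if the materials are equal.** With each discordant cell 0.012, Wald and score disagree in 11.6% of trials at 63 pairs, 11.8% at 64, and 7.0% at 65 and at 66.

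**5. Event definition (hypothetical).** Take 63 pairs with two TM Flow teeth at grade 2, one at grade 3 and all other teeth at grade 1. Counting grade 2 or higher gives 3 v 0 and a score limit of 11.3% (fails). Counting grade 3 or higher gives 1 v 0 and 6.8% (passes).

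**The case against.** The strongest reply is that the method can be inferred. The plan fixes a paired design, one-sided hypotheses, alpha, margin and a nuisance parameter, and of the methods tried only the paired score test returns 63. On that view Wald is an outside comparator, and the defect is only that the test used in 6.2 was not carried into 6.4.2. This stands as far as it goes, and it shows which repair fits the design. It does not replace prespecification: the inference depends on guessing the meaning of an undefined parameter, and 6.2 offers the calculations only on request.

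Other points:

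- **Literal reading.** The 44–61% figures treat 6.4.2 as a bare point-estimate rule, against the evident intent of 6.1 and 6.2. They are a conditional worst case. They do show that the sentence, followed as written, would not hold 5%.
- **Likelihood of the example.** A 2 v 0 table has about 6.4% probability under the planning assumption, and the disagreement rate falls from 11.6% to 7.0% at full enrolment. Both are correct, and both are too large to ignore for a primary claim.
- **Event definition.** Grade 1 is described as free of complaint and grade 2 as minor pain, so grade 2 or higher is the natural reading. It is nowhere stated. This is a secondary matter, separate from the missing test.
- **Unblinded analyst.** Outcomes are graded by a blinded evaluator (4.1, 4.2.2), which protects the grades. It does not protect a choice of method made after the data are seen.

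**Conclusion.** The concern holds and must be fixed before the primary analysis. The decision rule is not connected to the stated one-sided 5% alpha, and nothing elsewhere in the document fills the gap. An ordinary Wald limit would carry a false non-inferiority risk of 7.4–13.3%, above the planned 5% in every setting examined. The paired score limit stays at 3.3–5.1%. If the materials are truly equal, the two methods reach opposite conclusions in about 7–12% of trials at 63 to 66 pairs.

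These figures assume a dichotomised B3, 63 to 66 complete pairs and control-only discordance between 0 and 2.34%. The disagreement rate further assumes 0.012 in each discordant cell. The omission itself rests on none of these assumptions.

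**What to change.** Replace the decision sentence in 6.4.2 with: *Non-inferiority is concluded only if the upper limit of the one-sided 95% confidence interval for P_treat − P_control, computed from the paired 2×2 table by the score method for paired proportions (Tango/Nam), is below 7.6%.* Report the paired 2×2 table. An exact unconditional paired test is an acceptable alternative (at most 4.8% here, against 5.1% for the score method at 65 pairs). A plain Wald limit is not.

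Before any data are analysed, add one sentence stating which B3 grades at 1 month count as an event, and confirm that the 2.4% and 10% in 6.1 refer to that same event.

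The cost is SAP wording, an event definition and a short script. Power depends on what the nuisance parameter means, so 6.2 should define it:

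- If 0.012 is each discordant cell, exact score power is 84.9% at 63 pairs and 89.1% at 66, and no more patients are needed.
- Power stays at 80% up to a discordant cell of about 0.015 (63 pairs) or 0.0205 (66 pairs).
- If events in a patient's two teeth were independent (each cell 0.0234), power would be 69.5% and 77.0%. About 77 pairs would then be needed by exact power, against 83 by the asymptotic formula.
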